### **7.6.1. Grades 1 and 2 Laboratory Abnormality or Clinical Event**

Continue study drug at the discretion of the investigator.

### **7.6.2. Grade 3 Laboratory Abnormality or Clinical Event**

- For a Grade 3 clinically significant laboratory abnormality or clinical event, IMP may be continued if the event is considered to be unrelated to IMP.
- For a Grade 3 clinical event, or clinically significant laboratory abnormality confirmed by repeat testing, that is considered to be related to IMP, IMP should be withheld until the toxicity returns to  $\leq$  Grade 2.

- If a laboratory abnormality recurs to  $\geq$  Grade 3 following re-challenge with IMP and is considered related to IMP, then IMP should be permanently discontinued and the subject managed according to local practice. Recurrence of laboratory abnormalities considered unrelated to IMP may not require permanent discontinuation.

### **7.6.3. Grade 4 Laboratory Abnormality or Clinical Event**

For a Grade 4 clinical event or clinically significant Grade 4 laboratory abnormality confirmed by repeat testing that is considered related to IMP, IMP should be permanently discontinued and the subject managed according to local practice. The subject should be followed as clinically indicated until the laboratory abnormality returns to baseline or is otherwise explained, whichever occurs first. A clinically significant Grade 4 laboratory abnormality that is not confirmed by repeat testing should be managed according to the algorithm for the new toxicity grade.

Investigational medicinal product may be continued without dose interruption for a clinically non-significant Grade 4 laboratory abnormality (eg, Grade 4 creatine kinase [CK] after strenuous exercise or triglyceride elevation that is nonfasting or that can be medically managed) or a clinical event considered unrelated to IMP.

Treatment-emergent toxicities will be noted by the investigator and brought to the attention of the medical monitor, who will have a discussion with the investigator and decide the appropriate course of action. Whether or not considered treatment-related, all subjects experiencing AEs must be monitored periodically until symptoms subside, any abnormal laboratory values have resolved or returned to baseline levels or they are considered irreversible, or until there is a satisfactory explanation for the changes observed. Any questions regarding toxicity management should be directed to the medical monitor. The medical monitor should consult the medical leader as needed.

## **7.7. Special Situations Reports**

### **7.7.1. Definitions of Special Situations**

Special situation reports include all reports of medication error, abuse, misuse, overdose, occupational exposure, drug interactions, exposure via breastfeeding, unexpected benefit, transmission of infectious agents via the product, product complaints, counterfeit or falsified medicine, and pregnancy reports regardless of an associated AE.

Medication error is any unintentional error in the prescribing, dispensing, preparation for administration or administration of an investigational product while the medication is in the control of a health care professional, patient, or consumer. Medication errors may be classified as a medication error without an AE, which includes situations of missed dose; medication error with an AE; intercepted medication error; or potential medication error.

Abuse is defined as persistent or sporadic intentional excessive use of an investigational product by a subject.

Misuse is defined as any intentional and inappropriate use of an investigational product that is not in accordance with the protocol instructions or the local prescribing information.

An overdose is defined as an accidental or intentional administration of a quantity of an investigational product given per administration or cumulatively which is above the maximum recommended dose as per protocol or in the product labeling (as it applies to the daily dose of the subject in question). In cases of a discrepancy in drug accountability, overdose will be established only when it is clear that the subject has taken the excess dose(s). Overdose cannot be established when the subject cannot account for the discrepancy except in cases in which the investigator has reason to suspect that the subject has taken the additional dose(s).

Occupational exposure is defined as exposure to an investigational product as a result of one's professional or non-professional occupation.

Drug interaction is defined as any drug/drug, drug/food, or drug/device interaction.

Unexpected benefit is defined as an unintended therapeutic effect where the results are judged to be desirable and beneficial.

Transmission of infectious agents is defined as any suspected transmission of an infected agent through an investigational product.

Product complaint is defined as complaints arising from potential deviations in the manufacture, packaging, or distribution of the investigational product.

Counterfeit or falsified medicine: Any investigational product with a false representation of:  
a) its identity, b) its source, or c) its history.

## **7.7.2. Instructions for Reporting Special Situations**

### **7.7.2.1. Instructions for Reporting Pregnancies**

The investigator should report pregnancies in female study subjects that are identified after initiation of study drug and throughout the study, including the post study drug follow-up period, to DIVERSITYLTE\[contact] using the pregnancy report form within 24 hours of becoming aware of the pregnancy.

Refer to Section 7.3 and the eCRF completion guidelines for full instructions on the mechanism of pregnancy reporting.

The pregnancy itself is not considered an AE nor is an induced elective abortion to terminate a pregnancy without medical reasons.

Any premature termination of pregnancy (eg, a spontaneous abortion, an induced therapeutic abortion due to complications or other medical reasons) must be reported within 24 hours as an SAE. The underlying medical reason for this procedure should be recorded as the AE term.

A spontaneous abortion is always considered to be an SAE and will be reported as described in Section 7.3. Furthermore, any SAE occurring as an adverse pregnancy outcome post study must be reported to DIVERSITYLTE\[contact].

The subject should receive appropriate monitoring and care until the conclusion of the pregnancy. The outcome should be reported to DIVERSITYLTE\[contact] using the pregnancy outcome report form. If the end of the pregnancy occurs after the study has been completed, the outcome should be reported directly to DIVERSITYLTE\[contact].

Refer to Appendix 6 for Pregnancy Precautions, Definition for Female of Childbearing Potential, and Contraceptive Requirements.

#### **7.7.2.2. Reporting Other Special Situations**

All other special situation reports must be reported on the special situations report form and forwarded to DIVERSITYLTE\[contact] within 24 hours of the investigator becoming aware of the situation. These reports must consist of situations that involve study drug, but do not apply to concomitant medications.

Special situations involving concomitant medications do not need to be reported on the special situations report form; however, special situations that result in AEs due to a concomitant medication, must be reported as an AE.

Any inappropriate use of concomitant medications prohibited by this protocol should not be reported as “misuse,” but may be more appropriately documented as a protocol deviation.

Refer to Section 7.3 and the eCRF completion guidelines for full instructions on special situations reporting.

All clinical sequelae in relation to these special situation reports will be reported as AEs or SAEs at the same time using the AE eCRF and/or the SAE report form. Details of the symptoms and signs, clinical management, and outcome will be reported, when available.

## **8. STATISTICAL CONSIDERATIONS**

### **8.1. Analysis Objectives and Endpoints**

#### **8.1.1. Analysis Objectives**

The primary analysis objective is:

- To observe the long-term safety of filgotinib in subjects who have completed or met protocol specified discontinuation criteria in a prior filgotinib treatment study for CD

The secondary analysis objective is:

- To evaluate the effect of filgotinib on PRO2 and CDAI scores

[REDACTED]

- [REDACTED]  
[REDACTED]  
[REDACTED]
- [REDACTED]

### 8.1.2. Primary Endpoint

The primary end point is safety, evaluated through AEs, clinical laboratory tests, and vital signs.

### 8.1.3. Secondary Endpoint

The secondary end points are:

- Change from baseline in PRO2 and CDAI scores

[REDACTED] [REDACTED]

[REDACTED]

[REDACTED]  
[REDACTED]  
[REDACTED]

[REDACTED]

## 8.2. Analysis Conventions

### 8.2.1. Analysis Sets

#### 8.2.1.1. Safety/Efficacy

The primary analysis set for safety and efficacy is the Safety Analysis Set, which includes all enrolled subjects who received at least one dose of study drug.

[REDACTED] [REDACTED]

[REDACTED]  
[REDACTED]  
[REDACTED]

### 8.3. Data Handling Conventions

Values for missing safety laboratory data will not be imputed. If no pre-treatment laboratory value is available, the baseline value will be assumed to be normal (ie, no grade [Grade 0]) for the summary of graded laboratory abnormalities. If safety laboratory results for a subject are

missing for any reason at a time point, the subject will be excluded from the calculation of summary statistics for that time point.

Laboratory data that are continuous in nature but are less than the lower limit of quantitation (LLOQ) or above the upper limit of quantitation will be imputed to the value of the lower or upper limit minus or plus one significant digit, respectively (eg, if the result of a continuous laboratory test is < 20, a value of 19 will be assigned; if the result of a continuous laboratory test is < 20.0, a value of 19.9 will be assigned).

Procedure for handling missing data for PRO2 and CDAI scores will be described in the statistical analysis plan (SAP).

#### **8.4. Demographic Data and Baseline Characteristics**

Demographic and baseline measurements will be summarized using standard descriptive statistics (n, mean, standard deviation [SD], median, 1st quartile [Q1], 3rd quartile [Q3], minimum, maximum) for continuous variables and number and percentage of subjects for categorical variables.

Demographic summaries will include age, sex, race and ethnicity. Baseline characteristics may include height, weight, body mass index (BMI), PRO2 score, CDAI score, serum [REDACTED], [REDACTED], and other variables of interest.

#### **8.5. Efficacy Analysis**

Change from baseline in PRO2 and CDAI scores, and change in [REDACTED] will be summarized using standard descriptive statistics (n, mean, SD, median, Q1, Q3, minimum, maximum).

[REDACTED]

#### **8.6. Safety Analysis**

Safety will be evaluated by assessment of clinical laboratory tests, PEs, vital signs measurements at various time points during the study, and by the documentation of AEs.

All safety data collected on or after the first dose of study drug administration up to 30 days after the last dose of study drug will be summarized. All data collected during the course of the study will be included in data listings.

##### **8.6.1. Extent of Exposure**

A subject's extent of exposure to study drug will be generated from the study drug administration page of the eCRF. Exposure data will be summarized descriptively.

### **8.6.2. Adverse Events**

Adverse events will be coded using the Medical Dictionary for Regulatory Activities (MedDRA). System Organ Class (SOC), High-Level Group Term (HLGT), High-Level Term (HLT), Preferred Term (PT), and Lower-Level Term (LLT) will be attached to the clinical database.

Treatment-Emergent Adverse Events (TEAEs) are defined as 1 or both of the following:

- Any AEs with an onset date of on or after the study drug start date and no later than 30 days after permanent discontinuation of study drug
- Any AEs leading to premature discontinuation of study drug

Summaries (number and percentage of subjects) of TEAEs by SOC and PT will be provided. TEAEs will also be summarized by relationship to study drug and severity. In addition, TEAEs leading to premature discontinuation of study drug will be summarized and listed.

### **8.6.3. Laboratory Evaluations**

Selected laboratory data (using conventional units) will be summarized using only observed data. Absolute value and change from baseline at all scheduled time points will be summarized.

Graded laboratory abnormalities will be defined using the grading scheme defined in the CTCAE.

Incidence of treatment-emergent laboratory abnormalities defined as values that increase at least one toxicity grade from baseline at any time post baseline will be summarized. If baseline data are missing, then any graded abnormality (ie, at least a Grade 1) will be considered treatment emergent.

### **8.6.4. Other Safety Evaluations**

Individual data for PE findings, prior and concomitant medications and medical history will be provided. Vital signs measurements will be listed by subject and summarized by incidence of events/abnormalities or descriptive statistics as appropriate.

### **8.7. Pharmacokinetic Analysis**

Not applicable.

### **8.8.**

[REDACTED]

[REDACTED]

[REDACTED]

[REDACTED]

[REDACTED]

[REDACTED]

## 8.9. Sample Size

No formal hypothesis testing is planned for this study and sample size calculation is not conducted. All subjects who have completed or met protocol specified discontinuation criteria in a prior filgotinib treatment study for CD may enroll in this long-term extension study.

## 8.10. Interim Analysis

Interim analyses may be performed for regulatory submission purposes when the parent studies (GS-US-419-4015, GS-US-419-4016 and GS-US-419-3895) are unblinded. Further details of the interim analysis will be described in the SAP.

## 8.11. Data Monitoring Committee

While there are subjects receiving blinded treatment in this study, selected safety data from this study (DIVERSITY LTE) may be reviewed by the DMC for study GS-US-419-3895. After the present study is unblinded, safety monitoring will continue per the Sponsor's ongoing internal processes.

If the DMC recommends stopping the study for lack of efficacy, the Sponsor's Executive Team will be unblinded to confirm the DMC recommendation.

### Ad-hoc DMC Meetings

An ad-hoc convening of DMC may be triggered by the following condition:

- $\geq 2$  subjects develop any related, Grade 4, thromboembolic event that has been positively adjudicated by the adjudication committee (See Section 8.12)

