### 7.2.2. Assessment of Severity

The severity of AEs will be graded using the modified Common Terminology Criteria for Adverse Events (CTCAE), Version 4.03. For each episode, the highest grade attained should be reported.

If a CTCAE criterion does not exist, the investigator should use the grade or adjectives: Grade 1 (mild), Grade 2 (moderate), Grade 3 (severe), Grade 4 (life-threatening) or Grade 5 (fatal) to describe the maximum intensity of the adverse event. For purposes of consistency with the CTCAE, these intensity grades are defined in [Table 7-1](#) and [Appendix 5](#).

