**Table 7-1. Grading of Adverse Event Severity**

Grade	Adjective	Description
Grade 1	Mild	Asymptomatic or mild symptoms; clinical or diagnostic observations only; intervention not indicated
Grade 2	Moderate	Local or noninvasive intervention indicated; limiting age-appropriate instrumental ADL
Grade 3	Severe	Severe or medically significant but not immediately life-threatening; hospitalization or prolongation of hospitalization indicated; disabling; limiting self-care ADL
Grade 4	Life-threatening	Urgent intervention indicated
Grade 5	Death	Death related AE

\* Activities of Daily Living (ADL) Instrumental ADL refer to opening preparing meals, shopping for groceries or clothes, using the telephone, managing money, etc.

\*\* Self-care ADL refer to bathing, dressing and undressing, feeding self, using the toilet, taking medications, and not bedridden

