7.1.7.1. Summaries of AE incidence in Combined Severity Grade Subsets

A brief, high-level summary of the number and percentage of subjects who experienced at least 1 TEAE in the categories described below will be provided by treatment group. All deaths observed in the study will also be included in this summary.

The number and percentage of subjects who experienced at least 1 TEAE will be provided and summarized by SOC, PT, and treatment group. The same summary is provided for the other AE categories described below.

- TEAEs with Grade 3 or higher
- TEAEs with Grade 2 or higher
- Treatment-emergent (TE) treatment-related AEs
- TE treatment-related AEs with Grade 3 or higher
- TE treatment-related AEs with Grade 2 or higher
- TE SAEs
- TE treatment-related SAEs
- TEAEs leading to premature discontinuation of study drug
- TEAEs leading to premature discontinuation of study
- TE AEs leading to death (ie, outcome of death)
- TEAEs leading to temporary interruption of study drug

Multiple events will be counted only once per subject in each summary. Adverse events will be summarized and listed in descending order of frequency, first by SOC, then by PT and then alphabetically. For summaries by severity grade, the most severe grade will be used for those AEs that occurred more than once in an individual subject during the study.

In addition to the above summary tables, the following TEAEs will be summarized by PT only, in descending order of total frequency:

- TEAEs
- TEAEs with Grade 3 or higher
- TE SAEs
- TEAEs leading to premature discontinuation of study drug.

In addition, data listings will be provided for the following:

- All AEs, indicating whether the event is treatment emergent
- All SAEs
- All Deaths
- All SAEs leading to death (ie, outcome of death)

- All AEs with severity of Grade 3 or higher
- All AEs leading to premature discontinuation of study drug
- All AEs leading to premature discontinuation of study
- All AEs leading to temporary interruption of study drug

In addition, an XML file will be created to support EUDRACT reporting for the final analysis containing serious AEs, non-serious AEs and non-serious AEs occurring in at least 5% of subjects in at least one treatment arm, either at system organ class level or at PT level. (This XML file will be created in-house).

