7.1.8.1. Cardiovascular Safety Endpoint Adjudication Committee

An independent cardiovascular safety endpoint adjudication committee (CVEAC) was formed to periodically review and adjudicate all potential MACE and thromboembolic events in a blinded manner. To identify potential MACE and thromboembolic events, the following AEs were sent for adjudication. Refer to the Cardiovascular Event Adjudication Charter for more details.

- All AEs leading to death
- CV events (meeting seriousness criteria), utilizing an MST list developed by the Sponsor
- MI, utilizing a narrow scope SMQ
- Unstable angina (meeting hospitalization criteria), utilizing an MST list developed by the Sponsor
- Transient ischemic attack, utilizing an MST list developed by the Sponsor
- Stroke, utilizing an MST list developed by the Sponsor
- Cardiac failure (meeting hospitalization criteria), utilizing an MST list developed by the Sponsor
- Percutaneous coronary intervention, utilizing an MST list developed by the Sponsor
- Embolic and thrombotic events, utilizing a narrow scope SMQ

The CVEAC will review the above AEs, and related clinical data to adjudicate whether the criteria for MACE (CV death, MI, and/or stroke), ASTE, and VTE have been met for each AE.

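### The only ad-hoc DMC condition counts Grade 4 thromboembolic events alone, so fatal events (Grade 5) do not count towards it.

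*Protocol*

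**What the plan says.** The ad-hoc meetings paragraph of protocol Section 8.11 opens with "An ad-hoc convening of DMC may be triggered by the following condition" and then gives a single condition: two or more "subjects develop any related, Grade 4, thromboembolic event that has been positively adjudicated by the adjudication committee". No second condition follows, and the grade carries no wording that takes in anything above 4.

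The grading scale is set in Section 7.2.2. Where no CTCAE criterion exists, the investigator uses the five grades, ending in "Grade 4 (life-threatening) or Grade 5 (fatal) to describe the maximum intensity of the adverse event". Table 7-1 describes Grade 5 as "Death related AE". The recording rule is "For each episode, the highest grade attained should be reported", and SAP Section 7.1.2 repeats it. Appendix 5 makes only one change to the CTCAE, at Grade 1 for upper respiratory infection, so Grades 4 and 5 are unaltered.

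On other oversight, Section 8.11 says that, while some subjects are on blinded treatment, "selected safety data from this study (DIVERSITY LTE) may be reviewed by the DMC for study GS-US-419-3895". SAP Section 7.1.8.1 sends "All AEs leading to death" for cardiovascular adjudication.

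**The concern.** A trigger of this kind states in advance when a safety pattern should prompt the DMC to meet. Here the event is described by a single grade, and that grade is not the top of the scale. Because only the highest grade of an episode is recorded, a fatal embolism cannot also be counted as the life-threatening event it was before death. Anyone applying the condition to the recorded grades would leave it out.

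The result is an inverted ordering: two life-threatening, non-fatal events meet the condition and two deaths do not. What is at stake is a missed or delayed prompt to the DMC during blinded treatment. The risk is one the protocol takes seriously: the protocol history ties Amendment 7 to an FDA request about thromboembolic events with other JAK inhibitors, and Section 8.12 sets up an independent committee to adjudicate them. No estimate, endpoint or analysis is affected.

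**Working it through.** The plan gives no figure to reproduce here; Section 8.9 states that there is no hypothesis test and no sample size calculation. The check is a logical one.

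**Inputs**

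- Threshold: at least 2 subjects (Section 8.11).
- Qualifying event: related, Grade 4, thromboembolic, positively adjudicated (Section 8.11).
- Grade 4 is life-threatening and Grade 5 is fatal (Section 7.2.2, Table 7-1).
- One grade per episode, the highest (Section 7.2.2; SAP Section 7.1.2).
- Fatal events do go to adjudication (SAP Section 7.1.8.1), so adjudication does not keep them out. The grade does.

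**Step 1: grade pairs.** Take the first two subjects with a related, positively adjudicated Grade 4 or 5 event.

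| Pair | Number at Grade 4 | Met as written? | Met if Grade 5 also counts? |
|---|---|---|---|
| 4 + 4 | 2 | yes | yes |
| 4 + 5 | 1 | no | yes |
| 5 + 5 | 0 | no | yes |

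As written, 1 of 3 pairs meets the condition; with Grade 5 counted, 3 of 3 do. Pairs that include a Grade 3 event meet neither form.

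**Step 2: delay.** The count is cumulative. If k fatal events occur before the second Grade 4 event, the condition is met at subject 2 + k:

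- k = 0: 2nd subject
- k = 1: 3rd subject
- k = 2: 4th subject

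It is never met if fewer than two events are Grade 4. With Grade 5 counted it is met at the 2nd subject every time.

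**Step 3: illustration only.** The documents give no fatality rate. Assume that a share f of such events is fatal, independently between subjects. The probability that the condition as written is met is:

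- with 2 subjects: (1 − f)²
- with 3 subjects: 3f(1 − f)² + (1 − f)³

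| Assumed f | 2 subjects | 3 subjects |
|---|---|---|
| 10% | 0.81 | 0.97 |
| 25% | 0.56 | 0.84 |
| 50% | 0.25 | 0.50 |

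With Grade 5 counted, every entry is 1.00. The finding rests on Steps 1 and 2, not on these shares.

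**Step 4: is bare Grade 4 a shorthand?** Where the documents mean a threshold they generally write it out. SAP Section 7.1.7.1 tabulates "TEAEs with Grade 3 or higher", and protocol Section 7.6.2 uses at least Grade 3 for a recurring laboratory abnormality. Section 7.6.3 does name Grade 4 alone, but it concerns managing study drug in a living subject, where Grade 5 has no role. That reason does not carry over to a DMC trigger.

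**The case against.** The strongest reply accepts the literal reading and disputes its consequence.

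- **The condition is permissive and not said to be exclusive.** Nothing prevents the DMC from meeting after fatal events. This stands, and it is the main reason the gap is modest.
- **Deaths are seen elsewhere.** SAEs reach the Sponsor within 24 hours (Section 7.3.2). Section 5.1.1 allows safety-signal staff to be unblinded to cases or group summaries. SUSARs are reported outside the Sponsor (Section 7.4). Cardiovascular death is on the adjudication list (Section 8.12), and the Sponsor may terminate the study (Sections 3.5.2 and 9.3.4). This also stands: oversight of deaths is not lost. None of these routes, however, is a stated trigger for the DMC.
- **Delay is not demonstrated.** The condition waits for a committee that meets periodically, so it may not be the fastest route. That is fair as to calendar time. The delay shown above is in the number of subjects needed to meet the condition.
- **The drafting comparison is thin, and a slip for Grade 4 or higher is likely.** A slip is plausible, but no passage says so, and the text as it stands gives the wrong answer.
- **One in three pairs is not a probability.** Correct. The pairs are not equally likely, and the size in practice is unknown without a fatality rate.
- **The DMC charter is unseen and the window is limited.** Both stand. The DMC belongs to the parent study GS-US-419-3895. Many subjects are open-label from entry (Table 3-1), and after unblinding, monitoring passes to the Sponsor's internal processes (Section 8.11).

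**Conclusion.** The concern holds on the text. Nothing in the protocol or SAP brings Grade 5 into the condition. The conclusion assumes a literal reading of the grade and the highest-grade recording rule; it needs no event rate. Its weight is limited to a missed or late prompt to the DMC during blinded treatment, in a study where deaths are otherwise reported and adjudicated. Confidence in the textual finding is high. How often it would matter cannot be known from the documents. It should be corrected because a stated escalation threshold ought not to leave out the most severe outcome of the risk it was written for.

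**What to change.** Amend the ad-hoc condition in Section 8.11 so that fatal events count alongside life-threatening ones, for example by naming Grade 4 or Grade 5 in place of Grade 4. Leave the other elements (two subjects, relatedness, positive adjudication) as they are. Check the charter of the GS-US-419-3895 DMC. If it already includes Grade 5, bring the protocol into line with it; if not, change both together.

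The cost is a few words, a charter check and possibly one more DMC meeting. Because the DMC's role in this study is described only for the period of blinded treatment, the correction is useful only if it is in place while that period lasts.
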